**Exclusion criteria:**

- 1) Regular use of omega-3 nutritional supplements
- 2) Diabetes or fasting plasma glucose  $\geq 126$  mg/dL
- 3) Anemia (female subjects hemoglobin of  $\leq 11$  g/dL and male subjects hemoglobin  $\leq 12$  g/dL)
- 4) Active coronary artery disease or history of unstable macrovascular disease (unstable angina, myocardial infarction, stroke, and revascularization of coronary, peripheral or carotid artery within 3 months of recruitment)
- 5) Renal failure (serum creatinine  $> 1.5$  mg/dL)
- 6) Chronic active liver disease (AST  $> 144$  IU/L or ALT  $> 165$  IU/L)
- 7) Oral warfarin group medications or history of blood clotting disorders.
- 8) INR  $> 2.0$
- 9) Smoking
- 10) Pregnancy or breastfeeding
- 11) Alcohol consumption greater than 2 glasses/day or other substance abuse
- 12) Untreated or uncontrolled hypothyroidism
- 13) Debilitating chronic disease (at the discretion of the investigators)
- 14) Fish or shellfish allergy

**Consent and screening:** Potential participants will report to the Clinical Research and Trials Unit at Mayo Clinic Hospital St. Marys Campus the morning after an overnight fast. A member of the study team will meet the potential participant and the consent form will be read and discussed in private area. After receiving consent, the CRTU staff will measure vital signs including blood pressure, heart rate, temperature. Height and weight will be measured. The participant will undergo urine pregnancy test (if applicable) and screening blood work that will include CBC, lipid profile, creatinine, liver enzymes, TSH, glucose, insulin, blood clotting time (INR), c-reactive protein, and interleukin-6. Participants will be instructed on the use of a physical activity monitor (Actigraph), which they will wear for waking hours for a period of two weeks to quantify habitual physical activity levels. Participants will return for two additional blood draws and weight approximately 2 and 4 weeks later to repeat measurements of inflammatory markers (CBC, c-reactive protein, interleukin-6). Reconsenting may take place if study is stopped due to COVID closure. The subject will be withdrawn from the study at the point where the study stopped. The subject will be reconsented and start over from the beginning of the study.

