#### **D. Research Design and Methods:**

**Study Design:** Men and women between the ages of 20-35 years (N=30) and 65-85 years (N=120) will be recruited for this study. Participants in the older age group will be randomly assigned to receive n3-PUFA or placebo (corn oil) in a double-blind manner. Before and after the intervention, all participants will complete an outpatient study day (body composition, blood draw, treadmill test, strength test) and an inpatient study day (muscle biopsies, fat biopsies, indirect calorimetry, exercise test, mixed meal test) as described below in more detail. The DHA/EPA and placebo softgels will be supplied by Sancilio and Company, Inc., Riviera Beach, FL and stored in the Mayo Clinic Research Pharmacy at room temperature. During the intervention phase of the study, participants will be instructed to swallow 2 softgels twice per day with meals (morning and evening) for a total of 4 softgels per day. The DHA/EPA softgels will each contain 675mg of EPA and 300mg of DHA for a total daily dosage of 3.9g/day. The total omega-3 content of each capsule is 1050mg, which includes an additional 75mg of "non EPA/DHA" omega-3 fatty acids. The total fat content of the capsule will be 1200mg. This dose of EPA?DHA was chosen because it has been shown to augment the anabolic response of skeletal muscle [24] Every 4 weeks, participants will report to the Clinical Research and Trials Unit (CRTU) to pick up a new prescription and return any remaining capsules from the previous prescription. Remaining pills will be counted to determine compliance. The pharmacy will maintain records of receipt, dispensation, and return pill counts for compliance. Unused drug will be incinerated at the end of the study. On the day they pick up prescription refills, participants will report to the CRTU for a fasting blood sample to measure liver function (ALT, AST), coagulation (INR), blood lipid profile, glucose, and insulin. Participants will be withdrawn from the study if INR values exceed 2.0, indicating a high chance of bleeding. Participants will also be withdrawn from the study if ALT levels exceed 165IU/L or AST levels exceed 144IU/L. The duration of the intervention will be 6 months.

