**Participants:** Our plan is to complete the study on 120 men and women age 65-85yrs and 30 young adults who will only be studied at baseline. We are anticipating a target accrual of 179 subjects to account for an anticipated dropout rate of 20% in the intervention group.

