#### **Description of recruitment methods:**

We will use lists of prior research participants in our lab who have given permission to be contacted. We will use brochures, flyers, radio ads, television ads, and advertisements on the Research Studies section of the Mayo Classifieds. A member of the study team will contact participants by telephone or email with a brief description of the study and to determine if they are interested in participating. Brochures, flyers and radio ads will include the telephone number of a study team member. Participants will be asked to call the contact person. When the call is received, the member of the study team will perform a brief screening questionnaire to determine eligibility to proceed with enrollment. The screening questionnaire may also be sent by email in accordance with the Research Policy Manual Policy on Electronic Communications with Research

Subjects. The information gathered from the screening questionnaire will not be stored or used for data analysis if participants do not qualify for the study.

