At 0500h infusions of  $^{13}\text{C}_6$  phenylalanine at 1.0 mg/kg FFM/h and  $[^{15}\text{N}]$  tyrosine at 0.5 mg/kg FFM/h will be started after bolus of 1.0 mg/kg FFM  $[^{13}\text{C}_6]$  phenylalanine, 0.5 mg/kg FFM  $[^{15}\text{N}]$  tyrosine, and 0.5 mg/kg FFM  $[^{13}\text{C}_6]$  tyrosine. These are stable (non-radioactive) isotopes. Muscle biopsies from one *v. lateralis* will be obtained at 0830hrs for measuring baseline gene expression, protein expression, and mitochondrial function. Muscle biopsy samples will be collected under local anesthesia (2% lidocaine buffered with sodium bicarbonate) using a modified Bergstrom needle. A single abdominal subcutaneous fat biopsy will be performed at 0830 hrs under local anesthesia using sterile technique. Following the muscle and fat biopsies (~0900hrs), participants will perform a bout of unaccustomed unilateral knee extension exercise using only the leg without prior biopsies. Following a warm-up set, subjects will complete 8 sets of 10 repetitions at 70% of their 1-repetition maximum, determined at least 7 days prior. A second muscle biopsy will be obtained from the exercised leg 3 hours following exercise (~1230hrs).

Following the second biopsy (~1300hr), participants will consume a mixed liquid meal containing 15% protein, 55% carbohydrate, and 30% fat, approximately equal to 35% of resting energy expenditure determined from the REE on the outpatient study day. Arterialized blood samples will be taken from a heated hand vein for glucose, insulin, and c-peptide measurements at intervals over 5 h after the test meal, which will be consumed over 10 min. Blood samples will be collected at 30, 20, and 10 minutes before the meal and at 0, 5, 10, 15, 20, 30, 40, 50, 60, 75, 90, 120, 150, 180, 210, 240, 260, 280, and 300 minutes following the meal. We are collecting and washing red blood cells for storage for future testing. Resting energy expenditure and respiratory quotient will be measured by indirect calorimetry for 30 minutes under postabsorptive conditions (0700hrs) and postprandial (1430hrs). Participants will be given a meal from the hospital kitchen at approximately 1800hr before discharge.

The inpatient and 48 hour study day will be repeated following the 6 month intervention.

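### Criterion 7 excludes by drug only oral warfarin-group medications, so an older adult on another therapeutic anticoagulant with INR of 2.0 or below can be biopsied without meeting any named exclusion

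*Combined protocol and SAP*

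**What the plan says.** The Exclusion criteria contain 14 items, two of which concern coagulation. Criterion 7 is "Oral warfarin group medications or history of blood clotting disorders". Criterion 8 is an INR above 2.0. The Consent and screening paragraph lists "screening blood work that will include CBC, lipid profile, creatinine, liver enzymes, TSH, glucose, insulin, blood clotting time (INR), c-reactive protein, and interleukin-6", so INR is the only clotting test named at entry.

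During the intervention, the Study Design paragraph (section D) provides for a 4-weekly "fasting blood sample to measure liver function (ALT, AST), coagulation (INR), blood lipid profile, glucose, and insulin". Two laboratory withdrawal rules follow: "Participants will be withdrawn from the study if INR values exceed 2.0, indicating a high chance of bleeding" and "Participants will also be withdrawn from the study if ALT levels exceed 165IU/L or AST levels exceed 144IU/L".

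The inpatient study day includes a baseline muscle biopsy and an abdominal fat biopsy, and then "A second muscle biopsy will be obtained from the exercised leg 3 hours following exercise". A further muscle biopsy follows at 48 hours. The whole sequence is repeated after the 6-month intervention. Potential Risks (items d and f) lists hematoma for both kinds of biopsy. Item d describes pressure held until bleeding stops, then a pressure dressing.

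**The concern.** The only rule that acts on a drug covers one anticoagulant class. Everyone else is screened by clotting-disorder history and by INR. The trial enrolls people aged 65-85, and some volunteers of that age may take a non-warfarin anticoagulant for a reason that is not a clotting disorder. Applied as written, the criteria would admit such a person.

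What is at stake is participant safety, not the validity of a test. The biopsies are research procedures with no clinical indication, they are repeated, and the plan itself names hematoma as a hazard. The eligibility list is where it is decided who should have them.

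**Working it through.** There is no planned figure to reproduce. The check takes one person through every rule, then counts exposure and cost.

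**Test case (an assumption, for illustration).** A 70-year-old takes a non-warfarin therapeutic anticoagulant for a stable heart-rhythm indication. INR is 2.0 or below, ALT and AST are normal, and no other listed condition applies.

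| Rule | Where | Is it met? |
|---|---|---|
| Criterion 7, drug part | Exclusion criteria | No: not a warfarin-group drug |
| Criterion 7, history part | Exclusion criteria | No: the indication is not a clotting disorder |
| Criterion 8, INR above 2.0 | Exclusion criteria | No |
| Criterion 4, coronary and unstable vascular disease | Exclusion criteria | No: rhythm disorders are not named |
| Criterion 13, investigator discretion | Exclusion criteria | Only if a chronic disease is judged debilitating; it does not turn on a drug |
| Remaining criteria | Exclusion criteria | No: none names an anticoagulant |
| Withdrawal for INR, ALT or AST | Section D, Study Design | No |

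Two other steps could bring the drug to light. One is the recruitment contact, where "the member of the study team will perform a brief screening questionnaire to determine eligibility to proceed with enrollment". The other is the pretest history and examination in Potential Risks (e). Neither, as described, mentions anticoagulants or says what to do if one is found.

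**Biopsies for an older participant who completes the study.**
- From the study-day schedule: muscle at baseline, 3 h and 48 h = 3, plus 1 fat = 4 per round; 4 × 2 rounds = 8.
- From Human Subjects, Sources of Materials: 2 to 3 muscle plus 1 fat = 3 to 4 per round; × 2 = 6 to 8.
- That section ties its muscle count to the inpatient visit, while the 48-hour biopsy is an outpatient one. If the 48-hour biopsy is additional, the count is (2 to 3) + 1 + 1 = 4 to 5 per round, or 8 to 10 in total.

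About 4 per round is therefore a fair summary. These counts describe every older completer; they do not measure how many people fall into the gap.

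**Cost of a stricter rule.**
- Refill visits: 26 weeks / 4 = 6.5, so about 6.
- A participant who starts an anticoagulant mid-study and has no second biopsy round: 1/15 = 6.7% of a treatment-by-quartile cell, using the 15 per cell in Statistical analyses and Power.
- Room in accrual, from the Participants paragraph: 179 − 30 young adults = 149 older places; 149 − 120 = 29 spare; 29/149 = 19.5%; 29 / (4 quartiles × 2 arms) = 3.6 per cell. These places are already meant for the expected 20% dropout. The Human Subjects section gives a different completion total (135), so the margin is approximate.

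**The case against.** The strongest reply has four parts.

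1. *The hazard is not demonstrated.* The documents do not say how INR behaves under other anticoagulants or how often they cause biopsy bleeding. This stands: no bleeding rate can be given. The finding is only that the entry rule, as written, admits these people to procedures with a named hematoma risk.

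2. *The plan already protects against hematoma.* This stands in part. Potential Risks (d) presents pressure and dressing as means of making hematoma less likely, so they are preventive and do more than deal with a bleed that has happened. They still do not select who is biopsied.

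3. *The missing rule may be elsewhere.* The DSMP and short stretches of text around the study-visit descriptions were not available for this review. A drug-hold or stopping instruction could be there. A reader might infer that the plan has no rule at all for someone who starts an anticoagulant during the study; the available text cannot support that. The exclusion list, however, runs unbroken from 1 to 14, so the entry part can be judged.

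4. *Few people are affected.* Probably so. Criteria 4, 5, 7 and 13 will remove some likely users, and staff may notice others. This limits the weight of the point but does not close the gap.

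A reader might also infer that the plan itself regards a low INR as insufficient reassurance, because criterion 7 removes warfarin users whatever their INR. The protocol gives no reason for criterion 7. It could equally have been written to keep INR interpretable as the trial's 4-weekly safety test, so the argument does not rest on that inference.

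**Conclusion.** The point holds for entry. An older adult on a non-warfarin therapeutic anticoagulant, taken for a reason other than a clotting disorder and with INR of 2.0 or below, can meet no named exclusion. That person could then undergo about 4 biopsies per round in two rounds. The conclusion rests on the exclusion list being complete as shown and on reading the drug part of criterion 7 as it is worded.

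The number affected cannot be derived and may be zero. For a drug started during the study, the point is conditional: the visible withdrawal rules on safety grounds cover only INR, ALT and AST, but the DSMP and the text not seen may add to them. Antiplatelet drugs are outside this point. It is a worthwhile safety correction and has no bearing on the trial's power or primary inference.

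**What to change.** 1. Replace the drug part of criterion 7 with *any therapeutic anticoagulant (oral or injectable)*, and leave the clotting-disorder part as it is.
2. Confirm by medication history at the screening visit.
3. Unless the DSMP or other protocol text already covers it, ask about new anticoagulants at each 4-weekly refill visit. Next to the INR withdrawal rule, state that a participant who starts one has no further biopsies. If such an instruction already exists, a cross-reference from criterion 7 is enough.

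The cost is one reworded criterion, one sentence, and one question at visits that already take place (screening and about 6 refills). A few older volunteers become ineligible. An occasional second-round biopsy set is lost, each 1 of 15 (6.7%) in a treatment-by-quartile cell. Stopping biopsies without withdrawing the participant keeps the non-biopsy outcomes.

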At 0500h infusions of  $^{13}\text{C}_6$  phenylalanine at 1.0 mg/kg FFM/h and  $[^{15}\text{N}]$  tyrosine at 0.5 mg/kg FFM/h will be started after bolus of 1.0 mg/kg FFM  $[^{13}\text{C}_6]$  phenylalanine, 0.5 mg/kg FFM  $[^{15}\text{N}]$  tyrosine, and 0.5 mg/kg FFM  $[^{13}\text{C}_6]$  tyrosine. These are stable (non-radioactive) isotopes. Muscle biopsies from one *v. lateralis* will be obtained at 0830hrs for measuring baseline gene expression, protein expression, and mitochondrial function. Muscle biopsy samples will be collected under local anesthesia (2% lidocaine buffered with sodium bicarbonate) using a modified Bergstrom needle. A single abdominal subcutaneous fat biopsy will be performed at 0830 hrs under local anesthesia using sterile technique. Following the muscle and fat biopsies (~0900hrs), participants will perform a bout of unaccustomed unilateral knee extension exercise using only the leg without prior biopsies. Following a warm-up set, subjects will complete 8 sets of 10 repetitions at 70% of their 1-repetition maximum, determined at least 7 days prior. A second muscle biopsy will be obtained from the exercised leg 3 hours following exercise (~1230hrs).

Following the second biopsy (~1300hr), participants will consume a mixed liquid meal containing 15% protein, 55% carbohydrate, and 30% fat, approximately equal to 35% of resting energy expenditure determined from the REE on the outpatient study day. Arterialized blood samples will be taken from a heated hand vein for glucose, insulin, and c-peptide measurements at intervals over 5 h after the test meal, which will be consumed over 10 min. Blood samples will be collected at 30, 20, and 10 minutes before the meal and at 0, 5, 10, 15, 20, 30, 40, 50, 60, 75, 90, 120, 150, 180, 210, 240, 260, 280, and 300 minutes following the meal. We are collecting and washing red blood cells for storage for future testing. Resting energy expenditure and respiratory quotient will be measured by indirect calorimetry for 30 minutes under postabsorptive conditions (0700hrs) and postprandial (1430hrs). Participants will be given a meal from the hospital kitchen at approximately 1800hr before discharge.

The inpatient and 48 hour study day will be repeated following the 6 month intervention.

### 48 hours post-exercise biopsy:

Participants will return to the CRTU for an outpatient study visit involving an additional muscle biopsy from the exercised leg 48 hours following the single bout of exercise.

### Statistical analyses and Power:

For all variables in aim 1, the interest is in assessing if the change from baseline to post treatment differs by treatment arm. We will determine the influence of chronic inflammation on these outcomes in older adults grouped according to quartiles of a composite score including serum CRP and IL-6. The initial analysis will be stratified by inflammation composite score quartiles. Within a subgroup, the Wilcoxon rank sum test will be applied to test for difference in the change of outcome value pre and post treatment between the two treatment arms, placebo and n3-PUFAs. Additionally, generalized linear models will be used to assess the effect inflammation has on modifying the treatment effect by including interaction terms of a smoothing spline functional fit of the composite score with the treatment and time variables. The residuals from the regression will be used to assess distribution assumptions and variables will be transformed if required for appropriate statistical inference. All participants with at least a pre-treatment measurement will be included in the primary analysis utilizing the as-randomized study arm assignment for comparison. Efforts will be made to minimize missing data, but in the event of missing values, characteristics between those with observed values and with missing values will be compared. If no observed differences are identified, multiple imputation will be used with the primary analysis. Power calculations were performed for hypotheses related to mitochondrial physiology. We used the preliminary data where we measured effects of EPA on mitochondrial capacity. With mean  $JO_2 = 28.9 \text{ pmol/s/tissue}$  and  $\sigma = 4.891$ , a sample size of 15 per treatment group within an inflammation quartile gives 80% power ( $\alpha=0.05$ ) to detect a treatment difference in the difference from baseline to post treatment of  $5.18 \text{ pmol/s/tissue}$  (15% change). With 4 inflammation quartile groups, the total sample size will be 120, with

balanced randomization that gives 60 for each treatment arm in total. We believe that this expected difference is meaningful and realistic because our target population of older adults is known to exhibit reductions in mitochondrial capacity, and this degree of improvement would be physiologically important.

The main outcome variables for specific aim 2 are: 1) mRNA expression of anabolic and metabolic signaling genes, 2) expression and activation (phosphorylation) of signaling proteins, and 3) whole-body protein turnover. Hypothesis 2a will be addressed using the pre-treatment measurements, including a baseline and 3 post-exercise time points for all individuals. For each outcome, linear random effects models with time point and the inflammation score interaction terms plus a random intercept for each individual will be estimated. The statistical analysis for hypothesis 2b will be similar to specific aim 1, wherein regression models will be estimated for each outcome variable and include an interaction term between assigned treatment arm and the inflammation score. Missing data and loss to follow-up will be handled as described above in aim 1. Power calculations were performed using the preliminary data in which protein synthesis was measured using the same exercise protocol proposed in this aim. We utilized a linear random intercept model with a baseline and 3 post intervention time point and assuming an exchangeable correlation matrix with pairwise correlation of 0.7 within an individual between time points. With  $\sigma = 0.025 \text{ %/hr}$ , a sample size of 30 per inflammation group gives 80% power ( $\alpha=0.05$ ) to detect a  $0.028 \text{ %/hr}$  slope change between inflammation groups in muscle protein synthesis in response to exercise. We believe that this minimal detectable difference is meaningful, realistic, and conservative.

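### Aim 1 asks whether change differs by arm, but the only named arm tests are four within-quartile tests of raw change; baseline adjustment and a named overall contrast would add precision at no cost in data

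*Combined protocol and SAP*

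**What the plan says.** All of this is in section D of the combined protocol and SAP, under Statistical analyses and Power.

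- The question: "For all variables in aim 1, the interest is in assessing if the change from baseline to post treatment differs by treatment arm".
- The first analysis: "The initial analysis will be stratified by inflammation composite score quartiles". Inside each quartile the test is specified as follows: "Within a subgroup, the Wilcoxon rank sum test will be applied to test for difference in the change of outcome value".
- The second analysis: "Additionally, generalized linear models will be used to assess the effect inflammation has on modifying the treatment effect". It uses interactions of a spline of the composite score with treatment and time.
- The analysis population: "All participants with at least a pre-treatment measurement will be included in the primary analysis", by assigned arm. For missing data, on a stated condition, "multiple imputation will be used with the primary analysis". Neither sentence says which test or model is the primary one.
- The sample size: "a sample size of 15 per treatment group within an inflammation quartile gives 80% power" for a difference of 5.18 with sigma 4.891 and alpha 0.05. Four quartiles give 120 participants, with "balanced randomization that gives 60 for each treatment arm in total".

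In the text available, no contrast combining the quartiles, no baseline covariate and no multiplicity rule across quartiles is named.

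**The concern.** The stated question is about the two arms, yet no named test compares them as a whole. Each quartile test uses a quarter of the randomised older adults, and the model that uses all of them is given a different purpose. An analyst cannot tell which analysis takes the as-randomised population and the imputation. Nor does the plan say what to conclude if one quartile is significant and three are not.

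The outcome compared is raw change. When baseline and follow-up are imperfectly correlated, raw change is noisier than follow-up adjusted for baseline, although both estimate the same effect under randomisation. The baseline value is already collected, so that precision is available without any new measurement.

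**Working it through.** **Inputs from the plan.** 15 per arm per quartile, four quartiles, 60 per arm in total, sigma 4.891, difference 5.18, alpha 0.05, power 80%. Sidedness is not stated; two-sided reproduces the figure.

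**Assumed.** Pre-post correlation rho of 0.3, 0.5 or 0.7; equal pre and post variances; normal data; exact 15 v 15 balance in each quartile.

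**1. The plan's figure.** For a two-sample t-test with SD 4.891 and n = 15 per arm, power at 5.18 is 0.799 and the difference detectable at 80% power is 5.183. This matches 5.18, so 4.891 was used as the SD of change. Total: 15 x 2 x 4 = 120. The planned exact Wilcoxon test has simulated power of about 0.77 at 5.18.

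**2. Baseline adjustment.** The variance of change is 2s²(1 - rho). The residual variance of follow-up given baseline is s²(1 - rho²). Their ratio is (1 + rho)/2, so the SD shrinks by sqrt((1 + rho)/2).

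| rho | SD factor | adjusted SD | quartile: detectable (5.183 x factor) | quartile: power at 5.18 (27 df) | overall: detectable (2.522 x factor) |
|---|---|---|---|---|---|
| 0.3 | 0.806 | 3.94 | 4.18 | 0.93 | 2.03 |
| 0.5 | 0.866 | 4.24 | 4.49 | 0.90 | 2.18 |
| 0.7 | 0.922 | 4.51 | 4.78 | 0.86 | 2.33 |

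Of the rise from 77% to 86-93%, about 3 points come from using a t-type test in place of a rank test on normal data (77% to 80%). The rest comes from the baseline covariate.

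**3. Overall contrast.** With 60 v 60 and SD 4.891, the detectable difference is 2.522 unadjusted, about half of 5.183 (ratio 2.05). The last column above gives the adjusted values.

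**4. When pooling helps and when it does not.**

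- Shared effect of 2.52: one given quartile has about 25% power, the pooled unadjusted contrast about 80% and the pooled adjusted contrast 85-93%. The 80% holds by construction, because 2.52 is the pooled detectable difference.
- Shared effect of 5.18: at least one quartile is significant with probability 1 - (1 - 0.766)⁴ = 0.997.
- Effect of 5.18 in the top quartile only: the pooled adjusted contrast has about 33-37% power (31-39% in a second simulation), against about 77% for that quartile's Wilcoxon test.

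**5. Four tests.** The exact rank-sum test at 15 v 15 has size 0.0453. Under a global null, the chance of any significant quartile is 1 - (1 - 0.0453)⁴ = 0.169; simulation gives 16-17%.

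**6. Sensitivity to the meaning of 4.891.** If it is the SD of a single measurement, the SD of change is 4.891 x sqrt(2(1 - rho)) = 5.79, 4.89 or 3.79. The quartile detectable difference is then 6.13, 5.18 or 4.02 unadjusted. Adjusted, it is 5.183 x sqrt(1 - rho²) = 4.94, 4.49 or 3.70. The levels move; the variance ratio (1 + rho)/2 does not.

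**The case against.** The trial is built around inflammation. The hypotheses, the quartile grouping and the sample size all rest on it, and the plan calls its detectable difference realistic. At that difference in every quartile, the planned tests find at least one significant quartile more than 99% of the time. A pooled lead test would do worse than the plan if only the most inflamed benefit. Raw change is unbiased, and the gain from adjustment depends on a correlation that the plan does not give for this outcome. The only correlation in the document is 0.7, assumed for muscle protein synthesis in Aim 2; at that value the overall detectable difference moves only from 2.52 to 2.33.

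Most of this stands. It removes any case for imposing the pooled test as the lead, and it limits the pooling gain to shared effects smaller than 5.18. It does not supply an overall contrast for the question as stated, say what *primary analysis* means, or give a reason to leave the baseline value unused.

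A reader might infer more than the documents support:

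- *That no overall effect can be obtained.* The spline model contains treatment and time terms, so a contrast could be derived. The gap is that none is named.
- *That the plan has a 16-17% false-positive rate.* That needs a rule counting any significant quartile as a finding, and the plan states no such rule.
- *That the interaction test is weak because it rejects only 4-5% of the time under a shared effect.* With a shared effect there is no interaction, so this is its correct error rate.

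**Conclusion.** The point holds as a matter of lost precision and under-specification. It is not a bias, and it is not an error in the sample size, which reproduces.

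The firmest gain is baseline adjustment, which helps within quartiles at the plan's own 5.18 and overall. The quartile detectable difference falls from 5.18 (t-test) to 4.2-4.8. An overall contrast answers the stated question from data already planned, but it is worth most when the effect is shared and smaller than 5.18.

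The figures rest on reading 4.891 as the SD of change, the assumed rho range, equal pre and post variances, normality and balanced quartiles. Statements of absence apply to the text available. This is a free improvement, between minor and should-fix.

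**What to change.** 1. Replace the raw-change comparison with follow-up value on baseline value and arm, both within quartiles and overall. If a pre/post mixed model is preferred, constrain baseline means to be equal across arms. Without that constraint, a random-intercept model returns the raw-change estimate.
2. Add an overall arm contrast for mitochondrial capacity, the outcome used for the sample size, in all randomised older adults: follow-up on baseline, arm, and quartile or a spline of the score, two-sided 0.05. Apply the plan's as-randomised population and multiple imputation to it. Participants with only a pre-treatment value enter through that imputation, so also say what is done when its stated condition is not met.
3. Keep the spline-by-arm interaction as the test of effect modification, and report quartile effects with 95% confidence intervals.
4. State before analysis which is the lead: the overall contrast, a joint test of arm and arm-by-score, or the quartile tests. Tie *primary analysis* to it. The choice is the team's and should follow where benefit is expected. If the four quartile tests are read as claims, control the error rate across them.

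Hypothesis 2b is said to be analysed in a similar way to Aim 1, so the wording should carry over.

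**Cost.** Wording only, with no new participants or visits. A linear model replaces a rank test; residual checks and transformation are already planned. The sample-size justification stays at quartile level, with the pooled detectable difference added.
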